10. PHARMACOKINETICS

10.1 Collection of Plasma/Serum Samples for PK Analysis SAD

All PK analyses, summary tables and figures will be based on the PK set. All analyses will be summarized as described in section 3.1 (PK - continuous descriptive analysis). All listings will be based on the Safety set except for the PK parameter listings.

For SAD (Part 1, Cohorts 1, 2, 3a, 4, 5 and Cohort 3 FE), blood samples will be collected at Pre-dose (within 15 minutes prior to dosing) and at 0.5, 1, 1.5, 2, 3, 5, 8, 12, 16, 24-, 36-, 48-, and 72-hours post-dose. A blood sample will be collected prior to discharge in case of early termination.

Table 6 Collection of Blood Samples for PK Analysis in Single-Dose Cohorts

Sample Type	Dosing Day	Time Post-dose (hours).
Plasma	1	Pre-dose (within 15 minutes prior to dosing) and at 0.5, 1, 1.5, 2, 3, 5, 8, 12, 16, 24-, 36-, 48-, and 72-hours post-dose.

10.2 Collection of Plasma/Serum Samples for PK Analysis MAD

For MAD (Part 2), blood samples will be collected as follows: Day 1: Pre-dose (within 15 minutes prior to dosing) and at 0.5, 1, 1.5, 2, 3, 5, 8, 12, 16, and 24 (Day 2 pre-dose) hours post-dose. Day 3, Day 4, Day 5, and Day 6: Pre-dose (within 15 minutes prior to dosing). Day 7: Pre-dose (within 15 minutes prior to dosing) and at 0.5, 1, 1.5, 2, 3, 5, 8, 12, 16, 24, 36, 48, and 72 (a) hours post-dose. A blood sample will be collected prior to discharge in case of early termination.

Table 7 Collection of Blood Samples for PK Analysis in Multiple-Dose Cohorts

Sample Type	Dosing Day	Time Post-dose (hours).
Plasma	1	Pre-dose (within 15 minutes prior to dosing) and at 0.5, 1, 1.5, 2, 3, 5, 8, 12, 16, and 24 (Day 2 pre-dose) hours post-dose.
	3,4,5,6	Pre-dose (within 15 minutes prior to dosing)
	7	Pre-dose (within 15 minutes prior to dosing) and at 0.5, 1, 1.5, 2, 3, 5, 8, 12, 16, 24, 36, 48, and 72 ^(a) hours post-dose.

(a) If emerging PK data indicate the CVN766 $t_{1/2}$ is 15 hours (or less), the 72-hour timepoint is unnecessary.

10.5 Pharmacokinetic Parameters

Part 1 – Single Ascending Doses

The following pharmacokinetic parameters will, where possible, be determined from the plasma concentrations and CSF of analyte using non-compartmental methods via Phoenix WinNonlin Version 8.3 or higher.

Part 1 – Single Ascending Dose

Parameter	Definition
C_{max}	Observed maximum CVN766 concentration which is directly determined from the plasma concentration time profiles
T_{max}	Time to observed maximum observed CVN766 concentration. If the same C_{max} concentration occurs at different time points, T_{max} is assigned to the first occurrence of C_{max} .
T_{last}	Time to last observed CVN766 concentration.
AUC_{24}	The area under the plasma CVN766 concentration-time curve, from time 0 (time of dosing) to 24 hours, calculated by linear trapezoidal/ linear interpolation method
AUC_t	Area under the drug concentration-time curve, from time 0 (time of dosing) to the last measurable concentration using linear trapezoidal/ linear interpolation method
AUC_{inf}	The area under the plasma CVN766 concentration-time curve from time 0 (time of dosing) extrapolated to infinity. AUC_{inf} is calculated as the sum of AUC_t plus the ratio of the last measurable plasma concentration (C_{last}) to the elimination rate constant (λ_z), calculated by linear trapezoidal/ linear interpolation method.
$AUC_{\%extrap}$	The percentage of the AUC that has been extrapolated beyond the last observed data point, using the following formula, calculated by linear trapezoidal/ linear interpolation method $AUC_{\%extrap} = (AUC_{inf} - AUC_t) / (AUC_{inf}) * 100$
λ_z	Apparent terminal elimination rate constant calculated by linear regression of the terminal linear portion of the log concentration vs. time curve.
$t_{1/2}$	Apparent plasma terminal half-life calculated as $\ln(2) / \lambda_z$
CL/F	Apparent total plasma clearance, using the following formula $Dose / AUC_{inf}$
V_z/F	Apparent volume of distribution based on the terminal phase, reported to 3 significant figures and calculated as: $Dose / (\lambda_z \times AUC_{inf})$.
CSF:Plasma ratio	Ratio of the CVN766 concentration in CSF vs. the CVN766 concentration in plasma at 3h post dose.
DN_ C_{max}	Dose-normalized $C_{max} = C_{max} / dose$
DN_ AUC_{24hr}	Dose-normalized $AUC_{24hr} = AUC_{24hr} / dose$
DN_ AUC_t	Dose-normalized $AUC_t = AUC_t / dose$

DN_AUC _{inf}	Dose-normalized AUC _{inf} = AUC _{inf} /dose
-----------------------	---

Part 2 – Multiple Ascending Doses

All PK analyses, PK summary tables and figures will be based on the PK set. All analyses will be summarized as described in section 3.1 (PK - continuous descriptive analysis). All listings will be based on the PK set. All missing and BLQ handling of urine concentrations for PK analysis will be based on section 3.5.

Approximate attainment of steady state will be visually assessed by plotting mean C_{trough} concentrations.

The following pharmacokinetic parameters will, where possible, be determined from the plasma concentrations and CSF of analyte using non-compartmental methods via Phoenix WinNonlin Version 8.3 or higher.

Parameter at	Definition
Day 1	
C _{max}	Observed maximum CVN766 concentration in the dosing interval at Day 1
C _{min} ,	Observed minimum CVN766 concentration in the dosing interval at Day 1
C _{trough DayN}	Plasma concentration at the end of the dosing interval at day N, where N is Day 2,3,4,5,6,or 7
T _{max}	Time to reach maximum CVN766 concentration at Day 1
T _{min}	Time of minimum observed CVN766 concentration at Day 1
AUC _t	Area under the drug concentration-time curve, from time 0 (time of dosing) to the last measurable concentration at steady state using 'linear trapezoidal/ linear interpolation method' when t is < 24h. Determined following Dose on Day 7
AUC ₂₄	The area under the plasma CVN766 concentration-time curve, from time 0 to 24 hours, calculated by linear trapezoidal/ linear interpolation method. Determined following Dose on Day 1
CSF:Plasma ratio:	Ratio of the CVN766 concentration in CSF vs the CVN766 concentration in plasma at 3 h post dose
DN_C _{max,ss}	Dose-normalized C _{max,ss} = C _{max,ss} /dose
DN_AUC _{24hr}	Dose-normalized AUC _{24hr} = AUC _{24hr} /dose
DN_AUC _t	Dose-normalized AUC _t = AUC _t /dose

Parameter at Day 7	Definition
$C_{\max, ss}$	Observed maximum CVN766 concentration in the dosing interval at steady state at Day 7.
$C_{\min, ss}$	Observed minimum CVN766 concentration in the dosing interval at steady state at Day 7.
$C_{\text{trough Day}N}$	Plasma concentration at the end of the dosing interval at day N, where N is Day 2,3,4,5,6, or 7
$C_{\text{avg}, ss}$	Average steady state CVN766 concentration, determined following Dose on Day 7, using the following formula $C_{\text{avg}, ss} = \text{AUC}_{\text{tau}} / \text{tau}$ Where, tau = dosing interval
$T_{\max, ss}$	Time to reach maximum CVN766 concentration in the dosing interval at steady state at Day 7.
$T_{\min, ss}$	Time of minimum observed CVN766 concentration in the dosing interval at steady state at Day 7.
$T_{\text{last}, ss}$	Time of the last CVN766 concentration assessment in the dosing interval at steady state. Determined following Dose on Day 7
AUC_t	Area under the drug concentration-time curve, from time 0 (time of dosing) to the last measurable concentration at steady state using 'linear trapezoidal/ linear interpolation method' when t is < 24h. Determined following Dose on Day 7
AUC_{tau}	Area under the plasma CVN766 concentration-time curve over a dosing interval at steady state using the linear trapezoidal/ linear interpolation method. Determined following Dose on Day 7
AUC_{inf}	The area under the plasma CVN766 concentration-time curve from time 0 (time of dosing) extrapolated to infinity. AUC_{inf} is calculated as the sum of AUC_t plus the ratio of the last measurable plasma concentration (C_{last}) to the elimination rate constant (λ_z), calculated by linear trapezoidal/ linear interpolation method. Determined following dose on Day 1
λ_z or Kel	Apparent terminal elimination rate constant calculated by linear regression of the terminal linear portion of the log concentration vs. time curve. Determined following Dose on Day 7
$t_{1/2}$	Apparent plasma terminal half-life calculated as $\ln(2)/\lambda_z$. Determined following Dose on Day 1 and Day 7
CL/F_{ss}	Apparent total plasma clearance at steady state, using the following formula $\text{Dose}/\text{AUC}_{\text{tau}}$. Determined following Dose on Day 7
V_z/F_{ss}	Apparent terminal volume of distribution, calculated as: $\text{Dose}/(\lambda_z \times \text{AUC}_{0-\text{tau}})$. Determined following Dose on Day 7
$\text{RA}_{C_{\max}}$	Accumulation ratio based on C_{\max} in Part 2 calculated as $C_{\max, ss}$ on Day 7/ C_{\max} on Day 1 for each individual.
RA_{AUC}	Ratio of the measure of systemic drug exposure over a specific dosing interval at steady state to the measure of systemic drug exposure over a specific dosing interval after single dose administration. It is calculated as $\text{AUC}_{\text{tau Day 7}}/\text{AUC}_{24 \text{ Day 1}}$
CSF:Plasma ratio:	Ratio of the CVN766 concentration in CSF vs the CVN766 concentration in plasma at 3 h post dose
$\text{DN}_{C_{\max, ss}}$	Dose-normalized $C_{\max, ss} = C_{\max, ss}/\text{dose}$
DN_{AUC_t}	Dose-normalized $\text{AUC}_t = \text{AUC}_t/\text{dose}$
$\text{DN}_{\text{AUC}_{\text{tau}}}$	Dose-normalized $\text{AUC}_{\text{tau}} = \text{AUC}_{\text{tau}}/\text{dose}$
$\text{DN}_{\text{AUC}_{\text{inf}}}$	Dose-normalized $\text{AUC}_{\text{inf}} = \text{AUC}_{\text{inf}}/\text{dose}$

 C_{trough} determination for MAD cohorts:

C _{trough_Day1}	The pre-dose morning concentration observed on day 2 prior to the next dosing
C _{trough_Day2}	The pre-dose morning concentration observed on day 3 prior to the next dosing
C _{trough_Day3}	The pre-dose morning concentration observed on day 4 prior to the next dosing
C _{trough_Day4}	The pre-dose morning concentration observed on day 5 prior to the next dosing
C _{trough_Day5}	The pre-dose morning concentration observed on day 6 prior to the next dosing
C _{trough_Day6}	The pre-dose morning concentration observed on day 7 prior to the next dosing

C_{trough_Day1}, C_{trough_Day2}, C_{trough_Day3}, C_{trough_Day4}, C_{trough_Day5}, C_{trough_Day6} will be listed for each MAD cohort and dose level.

Additional pharmacokinetic parameters may be determined where appropriate.

Pharmacokinetic analysis will be carried out using actual doses and blood sampling times (post dose hourly sampling times for the specified days), where possible. If actual times are missing, nominal times may be used with sponsor approval.

Plasma, urine, and CSF concentrations of CVN766 will be used as supplied by the bioanalytical laboratory. The units of concentration and resulting PK parameters, with amount or concentration in the unit, will be presented as they are received from the bioanalytical laboratory.

If a PK parameter cannot be derived from a patient's concentration data, the parameter will be coded as NC (i.e., not calculated). NC values will not be generated beyond the day that a patient discontinues. If an individual patient has a known biased estimate of a PK parameter (due for example to a deviation from the assigned dose level and/or concomitant medication violation), this will be footnoted in summary tables and the parameter will not be included in the calculation of summary statistics or statistical analyses.

Pharmacokinetic Noncompartmental Analysis (NCA)

General Plasma NCA Pharmacokinetic Settings

The general settings in Phoenix WinNonlin® for generation of plasma PK parameters are as listed below.

- NCA Model Type: Plasma (200-202)
- Weighting: Uniform
- AUC Calculation Method: Linear trapezoidal/ linear interpolation method
- Dose Options Type: Extravascular
- Slopes Setting Fit Method: Best Fit/Visual Inspection
- Rsq_Adjusted Criteria for 'λ_z': 0.8
- AUC% extrapolation Criteria: 20

[figure not shown]

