3.5 Handling of Missing Data

For the classification of Treatment emergent adverse event (TEAE), Medical History and Concomitant medication, the following will be applied in the following order:

- If all dates/times (start and stop) missing, the event/medication will automatically be classified as a TEAE/Concomitant medication.
- For AEs with a missing start date/time, if the event end date/time is prior to first study drug administration, the event will not be classified as a TEAE.
- If only the AE start year/ medication end year is present and is the same or is after the first study drug administration year unit, the event/medication will be classified as a TEAE/Concomitant medication.
- If the AE start month and year/medication end month and year are present and are the same or after the first study drug administration month and year units, the event/medication will be classified as a TEAE/Concomitant medication.
- If start AEs, Concomitant Medication and Medical History Day is missing, it will be assigned as 1st Day of the Month. If AEs, Concomitant Medication and Medical History Month is missing, it will be assigned as 1st Month of the Year and if AEs, Concomitant Medication and Medical History Year is missing, Informed Consent Year will be used.
- If end AEs, Concomitant Medication and Medical History Day is missing, it will be assigned as 31st. If AEs, Concomitant Medication and Medical History Month is missing, it will be assigned as 12.

For the PK analysis the following will be applied:

- For the concentration descriptive summaries, concentrations may be excluded if sampling time deviation is considered large to affect the profile at the discretion of the pharmacokineticist.
- Concentrations that are below limit of quantification (BLQ) prior to the first quantifiable value will be set equal to zero. Post dose BLQ concentrations, post T_{\max} , will be set to missing.

- c. Where there are no results (NR), these will be set to missing.
- d. If more than 75% of values per nominal timepoint and treatment group are BLQ, then all descriptive statistics, except for nBLQ, will be denoted as not calculable (NC).
- e. For the calculation and graphical representation (semi-log and log-log plots) of geometric descriptive statistics, 0 values will be set to missing.

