- f. For the purpose of calculating the non-compartmental PK parameters, concentrations that are BLQ prior to the first quantifiable value will be set equal to zero. BLQ values after measurable concentrations will be set to missing. Concentrations in the terminal phase, which is preceded by two BLQ values, will be set to zero.
- g. For the calculation of summary statistics of PK parameters, all NR and NC values in a data series will be set to missing.

Conversion of categorical values

In some instances, continuous variables are expressed as a range (i.e., < 10). In such cases, values may be converted to the range boundary (upper or lower limit as applicable). As an example, a value of <10 may be converted to 10. Such substitutions will be clearly documented in the footnotes of relevant outputs.

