Summary of Plasma PK parameters

PK parameters will be determined for each analyte with intensive PK samplings. For the purpose of calculating the non-compartmental PK parameters, concentrations that are BLQ prior to the first measurable concentration value will be set equal to zero. BLQ values embedded between measurable concentrations will be set to missing. Concentrations that are BLQ in the terminal phase after the last measurable concentration will be set to missing.

It should be noted the imputation of BLQ for the determination of PK parameters is different from the BLQ imputation when PK concentrations are summarized. When PK parameters are estimated by a standard non-compartmental model, actual collection time will be used in the calculation of plasma PK parameters.

Goodness of Fit

- If data permits, the default ‘best fit’ method by Phoenix WinNonlin will be used for the selection of slopes to determine ‘ λ_z ’. If data do not permit, then the slope selection will be done by visual inspection or by a manual method to determine λ_z .
- When assessing terminal elimination phases, the R^2 adjusted value will be used as a measure of the goodness of fit of the data points to the determined line.
- Regression-based parameters (λ_z or k_{el} , AUC_{inf} , $AUC\%_{extrap}$, $t_{1/2}$, CL/F or CL/Fss, and V_z/F or V_z/F_{ss}) will only be calculated if the R^2 adjusted value of the regression line is greater than or equal to 0.8. If regression-based parameters cannot be calculated, they will be set to “NC”, defined as “not calculated” in the data listings and summary tables as appropriate.

Calculation of AUC

- The minimum requirement for the calculation of AUC will be the inclusion of at least 3 consecutive plasma concentrations above the lower limit of quantification (LLOQ), with at least one of these concentrations following C_{max} .
- All AUC values will be calculated using linear trapezoidal/ linear interpolation method

Period of Estimation

- Time period used for the estimation of $t_{1/2}$, where possible, will be over at least 2 half lives.
- Where an elimination half-life is estimated over a time period of less than 2 half-lives, it will be flagged in the data listings at the discretion of the pharmacokineticist, and the robustness of the half-life value and regression-based parameters (λ_z or k_{el} , AUC_{inf} , $AUC_{\%extrap}$, $t_{1/2}$, CL/F or CL/F_{ss} , and V_z/F or V_z/F_{ss}) should be discussed in the study report.

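### MAD Day 1 Cmin and Tmin are defined without excluding the pre-dose sample or the absorption phase, so as written Cmin is 0 at pre-dose for all 18 planned active participants

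*SAP*

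**What the plan says.** SAP section 10.5, in the Day 1 table for Part 2, defines Cmin as "Observed minimum CVN766 concentration in the dosing interval at Day 1" and Tmin as "Time of minimum observed CVN766 concentration at Day 1". The Tmin line does not even mention the dosing interval.

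Four other rules bear on the result:

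- **Sampling.** Section 10.2 (Table 7) gives the plasma schedule of the first dosing day as "Pre-dose (within 15 minutes prior to dosing) and at 0.5, 1, 1.5, 2, 3, 5, 8, 12, 16, and 24 (Day 2 pre-dose". The sample drawn before the dose is thus one of the Day 1 samples.
- **BLQ in deriving parameters.** Section 3.5, PK rule f, says that "concentrations that are BLQ prior to the first quantifiable value will be set equal to zero". Section 10.7 repeats it: "concentrations that are BLQ prior to the first measurable concentration value will be set equal to zero".
- **Start of the Day 1 profile.** Day 1 AUC24 is "The area under the plasma CVN766 concentration-time curve, from time 0 to 24 hours", so the time-0 value belongs to the profile.
- **Geometric statistics.** Under section 3.5, PK rule e, "0 values will be set to missing".

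Section 2.3 names Cmin among the multiple-dose secondary PK parameters, separately from steady-state Cmin. Mock Table 14.2.4.2 has Day 1 rows for both Cmin and Tmin.

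**The concern.** Before a first dose there is no drug in plasma. A minimum searched over a profile that begins with that sample will find it. The reported Day 1 Cmin would then record the absence of drug before treatment, not the lowest exposure during the dosing interval, and Tmin would record the pre-dose time.

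A programmer or pharmacokineticist who saw the column of zeros would probably change the rule. The SAP does not say which rule to use instead, so the choice would be made after the concentrations are known. At stake is a listed secondary parameter that is either uninformative or depends on an unwritten decision.

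**Working it through.** The SAP states no figure for this parameter, so there is nothing to reproduce. I applied its own rules.

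**1. Who is affected.** Section 2.1.2 plans 3 cohorts of 8, each with 6 on CVN766 and 2 on placebo. Active: 3 × 6 = 18. Placebo: 3 × 2 = 6. The PK set (section 4.1) requires at least one measurable plasma concentration, so the placebo participants are not expected in it.

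**2. Pre-dose sample included.** The pre-dose value is BLQ, precedes the first quantifiable value, and becomes 0. Quantifiable values are above 0, and BLQ values after a measurable one are set to missing. The minimum is therefore 0 and is found first at pre-dose. A simulation of first-dose one-compartment oral profiles on the SAP's Day 1 sampling grid gave Cmin = 0 and Tmin = 0 in 100% of profiles in all 32 scenarios, with 2,000 profiles each. Assumed ranges: half-life 3, 6, 15 and 30 h; absorption rate ka 0.5 and 2 per h; lag 0 and 0.5 h; LLOQ 0.1% and 1% of median Cmax. If actual sampling times are used, Tmin could read up to 15 minutes before dosing instead of exactly 0.

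**3. Geometric statistics.** With all values 0 and rule 3.5(e) setting zeros to missing, the geometric mean and geometric CV% of Day 1 Cmin have n = 0.

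**4. Post-dose samples only, no lag.** For first-order absorption and elimination, C(t) is proportional to exp(−kt) − exp(−ka·t), with k = ln 2 / half-life. The two candidates for the minimum are the 0.5 h sample, on the way up, and the 24 h sample, on the way down. The half-lives and ka below are assumptions.

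| Half-life | ka = 0.3 per h: C(0.5)/C(24) | ka = 1 per h: C(0.5)/C(24) | Lower sample |
|---|---|---|---|
| 24 h | 0.1250/0.4993 = 0.25 | 0.3791/0.5000 = 0.76 | 0.5 h |
| 12 h | 0.1108/0.2493 = 0.44 | 0.3650/0.2500 = 1.46 | depends on ka |
| 6 h | 0.0832/0.0618 = 1.35 | 0.3373/0.0625 = 5.40 | 24 h |

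The selected sample can also differ between participants with the same typical kinetics. In the simulation at a 15 h half-life, ka 0.5 per h and no lag, the post-dose minimum fell at 0.5 h in about 82% of profiles and at 24 h in about 18%.

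**5. Post-dose samples only, with a lag.** With a 0.5 h lag, the 0.5 h value is itself BLQ before the first quantifiable value and becomes 0. The simulation then gave Cmin = 0 with Tmin = 0.5 h in every profile. Removing the pre-dose sample alone does not repair the definition.

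**6. Where the value is used.** The accumulation ratios in section 10.5 use Cmax and AUC. The dose-proportionality, food and gender analyses in section 3.3 do not use Cmin. Ctrough_Day1 is the Day 2 pre-dose value, which is the 24 h sample. Day 1 Cmin and Tmin enter only summaries and listings.

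**The case against.** The strongest reply is that the pre-dose sample lies outside the interval. Cmin is taken within the dosing interval, the sample is drawn up to 15 minutes before dosing, and the Ctrough convention assigns each later pre-dose sample to the preceding day. On that reading the zero need not arise. This is a fair reading of the intent, but the SAP does not state it for Cmin, the Tmin line has no interval limit, and steps 4 and 5 show that the definition still does not identify a particular sample. At short half-lives without a lag it does return the 24 h value, as the 6 h row shows; the SAP gives no half-life on which to rely for that.

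The second reply is that little is lost, because Ctrough_Day1 already reports the 24 h concentration. That stands and limits the importance of the point.

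Several stronger inferences are tempting and are not supported:

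- **Division by zero in a Day 1 to Day 7 comparison.** No Cmin ratio is planned.
- **Cmin understated by 24% to 75%.** These figures are 1 − 0.76 and 1 − 0.25 from the 24 h row alone. They rest on one assumed half-life and on taking the 24 h value as the correct answer.
- **Conflicting geometric-mean entries.** Mock Table 14.2.4.2 shows N/A for Cmin at 45 mg and a placeholder at 125 mg. Similar inconsistencies occur for other parameters in the shells, so this is formatting and not evidence about how Cmin is meant.
- **Cmin,ss needs the same repair.** The Day 7 pre-dose sample follows six daily doses, so it is not zero by construction.

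**Conclusion.** The point holds as a defect in the definition of one descriptive Day 1 parameter and its time. As written, Day 1 Cmin is 0 at pre-dose for all 18 planned active MAD participants, and its geometric statistics have n = 0. This rests on the SAP's own definition, schedule and BLQ rules, and on a BLQ pre-dose sample in participants who have not yet received CVN766. On a post-dose reading the result depends on half-life, absorption rate and lag, none of which the document gives; the ratios shown above use assumed values and only illustrate the range.

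A reader might infer that the multiple-dose PK results as a whole are compromised. They are not: the accumulation ratios, Ctrough_Day1 and Cmin,ss are not affected in this way, nor are the safety analyses. The correction is still worth making before unblinding, because Cmin is a listed secondary parameter and the repair costs almost nothing.

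**What to change.** In section 10.5, do one of the following:

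1. Define Day 1 Cmin as the lowest concentration after Tmax up to and including 24 h, and Tmin as the time of that concentration.
2. Drop Day 1 Cmin and Tmin, and rely on Ctrough_Day1, the 24 h (Day 2 pre-dose) value. The day index then needs aligning: the Day 1 parameter table numbers Ctrough from Day 2 to 7, while the Ctrough determination table numbers it from Day 1 to 6. Section 2.3 should also say which parameter the plain Cmin refers to.

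Leave the Cmin,ss definition unchanged. Restricting it to pre-dose and post-Tmax samples could discard a true minimum if absorption lags and the concentration is still falling at 0.5 h on Day 7.

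The cost is one definition and, under option 2, the matching rows in Table 14.2.4.2 and Listing 16.2.6.3.2. No new data or samples are needed.

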2.1.2 Part 2 MAD is a Multiple-Dose Regimen

Approximately 24 healthy male and female subjects aged 18 to 55 will be enrolled in 1 of the 3 multiple-dose cohorts (designated as M1 through M3, respectively) in an ascending fashion. The dose levels planned to be studied in the multiple-dose regimen are 45, 125, and 250 mg CVN766 for multiple-dose cohorts M1 through M3, respectively. Each multiple-dose cohort will consist of 8 subjects randomized to CVN766 or placebo, whereby 6 subjects will receive a daily oral dose of CVN766, and 2 subjects will receive matching placebo for 7 days. Dosing will be administered in the fasting state; the SRG can change this if exposure is higher in the fed state. The planned dosing duration for the multiple-dose cohorts is 7 days. However, the duration may be increased to \leq 14 days if preliminary PK data suggest steady-state will not be achieved within 6 days of daily dosing.

On Day 1 subjects, will undergo safety monitoring and PK sampling from blood plasma through 24 hours post-dose and on Day 7, will undergo safety monitoring and PK sampling from blood plasma through 72 hours post-dose. Additionally, PK samples will be collected on Days 3, 4, 5 and 6 prior to the next planned dose. For cohort M1, on day 7 only, subjects will undergo PK sampling from CSF via lumbar puncture at 3 hours post dose and PK sampling from urine over 24 h on Day 1 and Day 7. CSF samples may also be taken from M2 and M3 cohorts at the SRG's discretion.

Figure 1: Study Design

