2.3 Endpoints

Primary endpoint(s)

The primary endpoints of this study will be the following:

- Percentage of subjects who experience at least one treatment-emergent adverse event (TEAE)
- Percentage of subjects with abnormal and clinically significant (CS) safety laboratory test results at least once post-dose
- Percentage of subjects with abnormal and CS electrocardiogram (ECG) test results at least once post-dose
- Percentage of subjects with abnormal and CS vital sign measurements at least once post dose

Secondary endpoints(s)

- Single-dose plasma PK parameters of CVN766 including time to maximum plasma concentration (T_{max}), area under the plasma concentration-time curve from time 0 to 24 (AUC_{24}) and time 0 to infinity (AUC_{inf}), and terminal elimination half-life ($t_{1/2z}$) Multiple-dose plasma PK parameters of CVN766 including C_{min} , C_{trough} , C_{max} , AUC from time 0 to the end of dosing interval (AUC_t), terminal elimination half-life ($t_{1/2z}$), accumulation ratio (R_{acc}), time to steady-state ($T_{ss,max}$), steady-state C_{max} ($C_{max,ss}$), and steady-state C_{min} ($C_{min,ss}$) Single-dose and multiple-dose CSF concentrations and CSF: plasma ratios of CVN766

Other endpoints(s)

- Change from baseline in safety laboratory and ECG test results and vital signs.
- Additional plasma PK parameters of CVN766: CL/F or CL/F_{ss} and Vz/F or Vz/F_{ss}

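### Several MAD PK definitions in SAP 10.5 are tied to the wrong dosing day, so Day 1 AUC_t, Day 1 half-life and the AUCinf shown under Day 7 have no consistent definition

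*SAP*

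**What the plan says.** All of this is in SAP 10.5, Part 2, unless another place is named.

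- **AUC_t.** The Day 1 table and the Day 7 table carry the same definition: an area at steady state, "when t is < 24h. Determined following Dose on Day 7". DN_AUC_t is derived from it on both days.
- **AUCinf.** It appears, with DN_AUCinf, only in the Day 7 table. It is AUC_t plus the last measurable concentration over lambda_z, "calculated by linear trapezoidal/ linear interpolation method. Determined following dose on Day 1".
- **lambda_z.** It is the slope of the "linear portion of the log concentration vs. time curve. Determined following Dose on Day 7".
- **Half-life.** It is ln(2)/lambda_z, listed only in the Day 7 table, but "Determined following Dose on Day 1 and Day 7".
- **Sampling.** Day 1 samples end at "8, 12, 16, and 24 (Day 2 pre-dose) hours post-dose" (10.2). Subjects "on Day 7, will undergo safety monitoring and PK sampling from blood plasma through 72 hours post-dose" (2.1.2).
- **Quality rules.** The NCA settings give "AUC% extrapolation Criteria: 20" with no stated consequence. Under 10.7, adjusted R-squared below 0.8 makes regression-based parameters not calculated. A half-life estimated over fewer than two half-lives is flagged and discussed, not excluded.
- **Use.** Sections 3.3 and 10.7 put AUC_t/Dose and t1/2z into the MAD Day 1 gender analysis.
- **Labels.** The Day 1 table lists DN_Cmax,ss. Section 2.3 attaches the symbol AUC_t to the "AUC from time 0 to the end of dosing interval", which 10.5 calls AUCtau.

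**The concern.** A programmer who follows the table headings and one who follows the definitions would compute different quantities under the same label. The fault reaches reported output. Table 14.2.4.2 shows AUC_t on Day 1 and AUCinf on Day 7, and its Day 1 part has no half-life row. Table 14.2.8.2 asks for a male/female comparison of half-life on Day 1 and on Day 7 and cites Listing 16.2.6.3.2 as its source, but that listing has no half-life column for either day.

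Three results are at stake: the descriptive Day 1 AUC_t and DN_AUC_t, the AUCinf and DN_AUCinf printed under Day 7, and two rows of the MAD Day 1 gender analysis. In addition, AUC%extrap is not among the MAD parameters in 10.5 or the shells, so a reader of the MAD output could not see whether the 20% setting had been met.

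**Working it through.** The SAP gives no figure on this point, so there is none to reproduce. The contradiction is textual. The arithmetic only sizes its effect.

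**Step 1: definitions against their headings**

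| Parameter | Table it sits in | Day in its definition | Day of its inputs |
|---|---|---|---|
| AUC_t, DN_AUC_t | Day 1 | Day 7 | Day 7 |
| AUCinf, DN_AUCinf | Day 7 | Day 1 | AUC_t and lambda_z: Day 7 |
| t1/2 | Day 7 | Day 1 and Day 7 | lambda_z: Day 7 only |
| AUC_t, lambda_z, AUCtau | Day 7 | Day 7 | consistent |
| AUC24 | Day 1 | Day 1 | consistent |

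Taken literally, the Day 1 row for AUC_t repeats the Day 7 row, and Day 1 half-life has no slope to come from.

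**Step 2: what AUCinf means if it is computed from Day 7 data**

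Assumptions: one compartment, linear kinetics, instant absorption, steady state by Day 7, k = ln2/t1/2. The half-lives are assumed, since the SAP gives none. Then AUCinf/AUCtau = 1/(1 − exp(−24k)).

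- t1/2 = 8 h: 1/(1 − 0.125) = 1.14, an excess of 14%.
- t1/2 = 12 h: 1/(1 − 0.25) = 1.33, an excess of 33%.
- t1/2 = 15 h: 1/(1 − 0.330) = 1.49, an excess of 49%.

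Under these assumptions AUCtau equals the single-dose AUCinf, so the same percentages measure the carry-over. A numerical check with first-order absorption (ka = 1 per h), the SAP's sampling times, linear trapezoids and lambda_z from the last three points gave Day 7 AUCinf over single-dose AUCinf of 1.18, 1.38 and 1.54.

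**Step 3: would Day 1 values from 24 h of sampling meet the SAP's own criteria?**

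*Extrapolation.* With instant absorption the share beyond 24 h is exp(−24k), which reaches 20% at t1/2 = 24 × ln2/ln5 = 10.3 h. The numerical check puts the limit at 9.4, 9.9 and 10.1 h for ka = 0.5, 1 and 2 per h. At ka = 1 the extrapolated share is 13.6% at 8 h, 20.3% at 10 h, 26.5% at 12 h and 34.6% at 15 h.

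*Two half-lives.* The longest half-life that fits is half the fitting window:

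- 5–24 h: 19/2 = 9.5 h
- 8–24 h: 16/2 = 8 h
- 12–24 h (the last three samples only): 12/2 = 6 h

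So both criteria are met up to about 8 h when the fit can start by 8 h post-dose. They are borderline from 8 to 10 h and missed above about 10 h.

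**Step 4: what does not depend on the faulty rows**

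MAD dose proportionality uses Cmax and AUC24 on Day 1, and Cmax,ss and AUCtau on Day 7. RA_AUC is Day 7 AUCtau over Day 1 AUC24. CL/Fss is dose over AUCtau. All of these carry the right day.

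**The case against.** The strongest reply is that these are labelling slips in secondary output, and that the SAP protects itself. Parameters are derived where possible and otherwise coded as not calculated, short-span half-lives are flagged, and the exposure measures that carry the MAD conclusions are correctly dated. A Day 1 AUCinf is also a legitimate single-dose quantity, so its fault is the wrong table and Day 7 inputs, not the choice of day. All of that is right, and it limits the impact. It does not supply a Day 1 definition of AUC_t or a Day 1 slope for half-life.

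A reader might go further and infer that Day 1 half-life and AUCinf are bound to fail the plan's quality criteria. The SAP does not support this, because it states no expected half-life. The 15 h in the footnote to Table 7 is only a cut-off at or below which the 72 h sample is unnecessary, and it covers any shorter value. The two-half-life rule only flags, and the 20% setting has no consequence attached.

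A reader might also infer that the dosing-interval AUC endpoint is ambiguous. Section 2.3 spells out the area in words and only the symbol is off. DN_Cmax,ss on Day 1 is likewise a slip, since Listing 16.2.6.3.2 already shows DN_Cmax there.

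**Conclusion.** The point holds as a contradiction over dosing days. It rests on the text alone and needs no assumption about half-life. It affects descriptive MAD tables and the MAD Day 1 gender comparison of AUC_t/Dose and t1/2z, not the primary safety endpoints or the main MAD exposure analyses.

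The 14% to 49% excess applies only if AUCinf is computed from Day 7 data, and it depends on the assumed half-lives and the one-compartment model. No size is given for the Day 1 AUC_t error, because the definition's restriction to times below 24 h leaves unclear which Day 7 area would be reported. Whether Day 1 estimates would be adequate remains open until the half-life is known.

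**What to change.** Define Day 1 AUC_t as the area from 0 to the last measurable concentration within 24 h of the Day 1 dose. Then choose one of two options, both sound:

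- **(a)** Delete AUCinf and DN_AUCinf from the MAD parameters, determine lambda_z and half-life on Day 7 only, and drop t1/2z from the MAD Day 1 gender analysis.
- **(b)** Define a Day 1 lambda_z from the 0–24 h samples, move AUCinf, DN_AUCinf and Day 1 half-life to the Day 1 table, report AUC%extrap, and state that values above the 20% criterion are excluded from summaries and models.

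In either case, relabel DN_Cmax,ss on Day 1 as DN_Cmax and the dosing-interval AUC in 2.3 as AUCtau. Align Tables 14.2.4.2 and 14.2.8.2 and Listing 16.2.6.3.2, adding the missing half-life column.

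The cost is wording in the SAP and shells. Option (a) loses little: the planned MAD doses of 45, 125 and 250 mg are all SAD doses, where AUCinf and half-life come from sampling to 72 h. Option (b) keeps Day 1 estimates that may be valid if the half-life is short, at the cost of a few more rows and an exclusion rule.
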